### **3.2.3 Mapping of assessments performed at Early Termination Visit**

Efficacy and safety assessments at an ETV that correspond to a scheduled visit will be summarized at the scheduled visit corresponding to the ETV if the assessment was scheduled to occur at that visit.

In particular, clinical laboratory parameters, vital signs, and body weight are assessed at all visits during the Treatment Period, and so all assessments of these variables at ETVs corresponding to a scheduled visit will be mapped to the corresponding scheduled visit.

### **3.2.4 Last Visit**

The Last Visit for all assessments is the last non-missing assessment during the Treatment Period. All scheduled and unscheduled assessments within this time period will be considered. Last Visit will be determined separately for each study procedure where Last Visit is mentioned within this document.

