### 2.3 Study design and conduct

This is a Phase 3, multicenter, double-blind, randomized, placebo-controlled, parallel-group study to evaluate the efficacy and safety of LCM (LCM 8mg/kg/day to 12mg/kg/day [oral solution] for subjects weighing <30kg, LCM 6mg/kg/day to 8mg/kg/day [oral solution] for subjects weighing  $\geq$ 30kg to <50kg, and LCM 300mg/day to 400mg/day [tablets] for subjects weighing  $\geq$ 50kg, or matching placebo) as adjunctive therapy in subjects with epilepsy  $\geq$ 4 years to <17 years of age with uncontrolled partial-onset seizures. Subjects weighing  $\geq$ 50kg who are unable or unwilling to swallow tablets may receive LCM oral solution. However, they are not permitted to exceed the maximum dose of LCM 400mg/day.

A total of approximately 300 subjects are planned to be randomized at approximately 155 sites. The study will be conducted in the [REDACTED] region with the possibility to expand the study to other countries and regions if deemed necessary.

Stratification of subjects by age category is planned to ensure that an appropriate number of subjects will be included in each age range. The age categories are as follows:

- At least 100 subjects  $\geq$ 4 years to <12 years of age
- At least 100 subjects  $\geq$ 12 years to <17 years of age

Subjects with uncontrolled partial-onset seizures will be enrolled into an 8-week Baseline Period. At the end of the Baseline Period (Visit 2), eligible subjects will be randomized in a double-blind manner to 1 of 2 parallel treatment arms: LCM or placebo in a 1:1 ratio. At the end of Visit 2, subjects should take the first dose of study medication while in the clinic. At each subsequent clinic visit, subjects should take study medication (and any concomitant AEDs) at the regular times. Study medication will be administered orally bid at approximately 12-hour intervals in the morning and in the evening.

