#### Baseline Period

On or after the date of Visit 1 (entry to study) and prior to the date of first dose of study medication.

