#### Treatment Period

On or after the date of first dose of study medication and prior to or on the end date of the Treatment Period (Visit 8) for subjects who complete the Treatment Period, or on or after the date of first dose of study medication and prior to or on the date of the ETV for subjects who discontinue during the Treatment Period. If a subject does not have a Visit 8/ETV, then either the date of the last scheduled or unscheduled visit during the Treatment Period or the date of last known dose of study medication during the Treatment Period, whichever is later, will define the end date of the Treatment Period.

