### 3.3 Definition of Baseline values

In general, Baseline values for efficacy and safety variables will be determined from the last non-missing scheduled or unscheduled assessment prior to the first dose of study medication, unless otherwise noted for a specific type of data.

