#### 10.4.9 BRIEF-P and BRIEF assessment

The BRIEF-P/BRIEF assessments are completed at Visit 2 (Baseline), Visit 8, and at ETV in case of early termination.

The BRIEF-P and BRIEF are validated tools that will be used for the evaluation of subjects  $\geq 2$  to  $< 5$  years of age, and  $\geq 5$  years of age, respectively. For each subject, the same version (BRIEF-P or BRIEF) that is used at Visit 2 (Baseline) should be used at Visit 8/ETV.

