## Change #7

### Section 3.2.4 Last Value on study medication

The Last Value on study medication for all assessments is the last available result obtained after first dose of study medication and prior to or on the last dose of study medication. All scheduled and unscheduled assessments within this time period will be considered. Last Value will be determined separately for each vital sign, ECG, and laboratory parameter.

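### As written, Last Visit can be the pre-dose Visit 2 value, so a subject with no later value enters the Last Visit summaries as unchanged from Baseline

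*SAP*

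**What the plan says.** SAP 3.2.4 gives one definition for every procedure: "The Last Visit for all assessments is the last non-missing assessment during the Treatment Period". It adds: "All scheduled and unscheduled assessments within this time period will be considered". No condition refers to time after the dose or after Baseline.

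Three other SAP provisions decide what this covers on the day of Visit 2:

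- Treatment Period (SAP 3.2.2): "On or after the date of first dose of study medication and prior to or on the end date of the Treatment Period", for subjects who complete it. The start is the same for those who discontinue. This is a rule on dates, with no time of day.
- Baseline Period (SAP 3.2.2): "On or after the date of Visit 1 (entry to study) and prior to the date of first dose of study medication".
- Timing of the first dose (SAP 2.3): "At the end of Visit 2, subjects should take the first dose of study medication while in the clinic".

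The Baseline value itself is, in general, the "last non-missing scheduled or unscheduled assessment prior to the first dose of study medication" (SAP 3.3).

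The schedule matters too. For the cognitive scales, "The BRIEF-P/BRIEF assessments are completed at Visit 2 (Baseline), Visit 8, and at ETV in case of early termination" (SAP 10.4.9). PedsQL (SAP 8.3.3) and endocrinology (protocol Table 5-1) follow the same pattern within the Treatment Period. So does the complete neurological examination (SAP 10.4.4.1), which is also done at Visit 1.

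**The concern.** A Last Visit summary should show the last value each subject had on treatment. Under the date rules, the Visit 2 value qualifies whenever nothing later exists. The same number then serves as both Baseline and endpoint, and a subject with no on-treatment information is tabulated as having no change or no shift.

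For measures taken only at Visit 2 and at Visit 8 or early termination, Last Visit is where most early leavers are picked up. SAP 3.2.3 maps an early-termination value to a scheduled visit only if the assessment was due at that visit. For the complete neurological examination, the Baseline-to-Last-Visit shift table is the only planned tabulation; abnormal findings are otherwise listed. Filling it with Baseline records understates worsening and overstates the number of subjects assessed.

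**Working it through.** The plan states no figure for this, so the check is a reading of the rules followed by a simple dilution formula.

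**Step 1: place the Visit 2 value.** The first dose is planned for the end of Visit 2, so the date of Visit 2 is the date of first dose. The Baseline Period stops before that date and the Treatment Period starts on it. A Visit 2 assessment is thus pre-dose but dated within the Treatment Period.

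**Step 2: apply Last Visit.** If any later non-missing value exists, it is chosen and no harm is done. If none exists, Last Visit is the Visit 2 value. Under SAP 3.3 that is also Baseline, so change = Visit 2 − Visit 2 = 0, and a shift table shows no shift.

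**Step 3: see whether other sections close the gap.** For marked laboratory and vital-sign abnormalities, SAP 10.3 and 10.4.1 require values on or after the first administration. SAP 10.4.2 requires a post-Baseline visit for treatment-emergent ECG abnormalities. SAP 3.2.4 has no such condition, so the change and shift summaries at Last Visit are not protected.

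**Step 4: sort the measures.**

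- Most exposed: BRIEF-P/BRIEF, PedsQL, endocrinology and the complete neurological examination. Height and BMI share this schedule.
- Little exposed: hematology and chemistry, vital signs, body weight and ECG, which have several on-treatment visits. ECG Baseline is the average of all pre-dose readings (SAP 10.4.2), so its change would not in general be exactly zero.
- Not affected: Tanner stage and head circumference (no Visit 2 assessment), the two Global Impression of Change scales (no Baseline value), and the seizure-frequency analyses (they do not use Last Visit).

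**Step 5: size.** Let f be the share of Last Visit records that are really Visit 2 values. Then

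reported mean change = (1 − f) × mean change among subjects with a post-dose value + f × 0.

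The percentage with a shift is multiplied by the same (1 − f). Write f = d × m, with d the dropout rate and m the share of dropouts with no post-dose value. This assumes that everyone has a Visit 2 value and that all other subjects have a later one. The plan gives d = 14% for sample size and a maximum of 24% in the re-estimation (SAP 2.4 and 2.4.1). It gives no m.

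| d | m (assumed) | f | multiplier | subjects of 154 per arm |
|---|---|---|---|---|
| 14% | 5% | 0.7% | 0.993 | 1.1 |
| 24% | 10% | 2.4% | 0.976 | 3.7 |
| 14% | 100% (ceiling) | 14% | 0.86 | 21.6 |
| 24% | 100% (ceiling) | 24% | 0.76 | 37.0 |

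The ceiling rows would need every dropout to lack a later value. They are not forecasts.

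**The case against.** The best defence is that the intent is plain. The SAP repeatedly labels Visit 2 as Baseline, and protocol Table 5-1 puts it in the Baseline Period. Change summaries are planned for post-Baseline visits and Last Visit, and a shift from Baseline to Last Visit presupposes two different assessments. A careful programmer might never carry the Baseline record forward. That is a fair account of the probable intent, but the operative rules are written by date, and the SAP states the post-dose condition in other sections where it wants one. As history only, the SAP amendment log shows that the superseded definition used the "last available result obtained after first dose of study medication and prior to or on the last dose of study medication". That makes an accidental omission plausible.

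The second defence is that few subjects can be affected. Protocol 8.8 requires an Early Termination Visit for every withdrawal, with BRIEF, PedsQL, endocrinology and the complete neurological examination all included. This largely stands, and it is why the likely effect is small. It does not bring the number to zero. Protocol 6.3 provides for loss to follow-up, SAP 3.2.2 has a rule for subjects with neither Visit 8 nor an Early Termination Visit, and a PedsQL scale is not scored if fewer than half its items are answered (SAP 8.3.3).

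A reader might also infer that Last Visit is the only summary that includes early leavers. The documents do not support that. By-visit summaries include anyone seen at the visit, SAP 3.2.3 maps early-termination laboratory, vital-sign and weight values to scheduled visits, and adverse event tables cover the whole Safety Set. Clinically significant neurological findings are also reported as adverse events.

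**Conclusion.** The gap is real. Followed literally, SAP 3.2.4 lets a Baseline value stand as an on-treatment value and produces a spurious zero change or no shift. The consequence is confined to descriptive change and shift summaries, chiefly those for BRIEF-P/BRIEF, PedsQL, endocrinology and the complete neurological examination. It assumes that the first dose is taken on the Visit 2 date, as planned.

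The size cannot be determined from the documents. An f of 0.7% to 2.4% is an illustration resting on an assumed 5% to 10% of dropouts with no post-dose value. A reader might suppose a share of 20% to 50% instead, giving 0.14 × 0.20 = 2.8% up to 0.24 × 0.50 = 12%. Nothing in the documents supports so high a share, given the mandatory visit. The 14% and 24% are overall-study dropout rates and may include subjects who left after Visit 8, so they only bound f from above. Nor do the documents show that one arm would be diluted more than the other: no completion rates by arm are given.

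**What to change.** Reword SAP 3.2.4 along these lines: *Last Visit is the last non-missing assessment obtained after the first dose of study medication and on or before the end of the Treatment Period. Visit 2 values, and any value used as Baseline, are never Last Visit. Subjects with no such value are not included.* Apply the matching filter in the derivation before unblinding.

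The cost is one clause, one filter and a slightly smaller n at Last Visit. Study conduct and the seizure-frequency analyses do not change.

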### 3.3 Definition of Baseline values

In general, Baseline values for efficacy and safety variables will be determined from the last non-missing scheduled or unscheduled assessment prior to the first dose of study medication, unless otherwise noted for a specific type of data.

### 3.4 Protocol deviations

Important protocol deviations are deviations from the protocol which could potentially have a meaningful impact on either the primary efficacy outcome or key safety outcomes for an individual subject. The criteria for identifying important protocol deviations and the classification of important protocol deviations will be defined separately in an important protocol deviations document. To the extent feasible, rules for identifying protocol deviations will be defined without review of the data and without consideration of the frequency of occurrence of such deviations. Whenever possible, criteria for identifying important protocol deviations will be implemented algorithmically to ensure consistency in the classification of important protocol deviations across all subjects.

In general, protocol deviations will be considered according to the following general categories:

- Inclusion criteria
- Exclusion criteria
- Withdrawal criteria
- Prohibited concomitant medications
- LCM dosing regimen
- Procedural non-compliance

Important protocol deviations will be reviewed as part of the blinded Data Evaluation Meetings (DEMs) prior to unblinding of the database. A list of subjects with important protocol deviations will be agreed upon during the DEMs and will be documented in the DEM minutes.

### 3.5 Analysis sets

The analysis sets defined for this study are the Safety Set (SS), Full Analysis Set (FAS), Per Protocol Set (PPS), and Pharmacokinetic Per Protocol Set (PK-PPS).

The primary analysis for the efficacy data will be the FAS. The secondary analysis set for the efficacy data will be the PPS. The primary analysis set for the safety parameters is the SS. The primary analysis set for the PK parameters is the PK-PPS.

#### 3.5.1 Safety Set

The SS will include all randomized subjects who took at least 1 dose of study medication.

#### 3.5.2 Full Analysis Set

The FAS will include all subjects who were randomized, received at least 1 dose of study medication, and had a Baseline and at least 1 post-Baseline assessment of seizure frequency data.

### **3.5.3 Per Protocol Set**

The PPS includes all subjects in the FAS who did not have important protocol deviations considered to have an impact on efficacy as confirmed during a DEM conducted prior to study unblinding.

### **3.5.4 Pharmacokinetic Per Protocol Set**

The PK-PPS will consist of all subjects having provided at least 1 measurable post-dose plasma sample (with recorded sampling time) on at least 1 visit with documented study medication intake times.

## **3.6 Treatment assignment and treatment groups**

It is expected that subjects will receive treatment as randomized. Thus, treatment assignment for the FAS and the SS will be according to randomization. However, if after unblinding it is determined that the subjects received treatment other than what they were randomized to receive, the safety analyses will be conducted using treatment assignments according to the actual treatment received (SS-as treated).

All subjects treated in this study receive study LCM at doses ranging from 8mg/kg/day to 12mg/kg/day (oral solution) for subjects weighing <30kg, 6mg/kg/day to 8mg/kg/day (oral solution) for subjects weighing  $\geq$ 30kg to <50kg, 300mg/day to 400mg/day (tablets) for subjects weighing  $\geq$ 50kg, or matching placebo. The subject's body weight at Baseline (Visit 2) will be used to determine dose throughout the study. Summaries will be presented based on treatment group; Placebo and LCM, and will generally not be differentiated by LCM dose. Where appropriate, LCM dose will be presented in subject data listings.

### **3.7 Center pooling strategy**

All centers will be pooled by country for the purpose of analysis.

### **3.8 Coding dictionaries**

Medical history and AEs will be coded using the Medical Dictionary for Regulatory Activities (MedDRA® v16.1). Medications will be coded using the World Health Organization Drug Dictionary (WHODD SEP/2013). Medical procedures will not be coded.

### **3.9 Changes to protocol-defined analyses**

There are no changes to analyses specified in the protocol.

## **4 STATISTICAL/ANALYTICAL ISSUES**

### **4.1 Adjustments for covariates**

An analysis of the primary efficacy variable and analyses of several other efficacy variables will be adjusted for Baseline seizure frequency and pooled center.

### **4.2 Handling of dropouts or missing data**

#### **4.2.1 Missing data**

For subjects who discontinue prior to the Maintenance Period, all available seizure frequency data will be carried forward from the Titration Period for the Maintenance Period analysis. For subjects who prematurely discontinue during the Maintenance Period, all available seizure

frequency data in the Maintenance Period will be carried forward for the entire Maintenance Period.

Subjects who discontinue prior to any efficacy data collection will not be included in the analysis (ie, data will not be carried forward from Baseline). The imputation for the seizure frequency data will not carry forward into the Transition and Taper Periods.

No imputation of missing values associated with an individual date or visit is planned for the primary safety analysis, with the exception of partial date information for AEs and concomitant medications in order to determine whether the AEs are treatment-emergent or the medications are concomitant.

With respect to AEs, events with missing intensity will be assumed to be severe. Events with missing relationship to study medication per the investigator will be assumed to be related. Incomplete or missing dates for events will be handled as described in section 3.2.2.

#### **4.2.2 Incomplete dates for adverse events and concomitant medications**

For analyses of AEs and concomitant medication usage, a complete date must be established in order to correctly identify the AE or medication as occurring during treatment or not. For purposes of imputing missing components of partially-reported start and stop dates for AEs and for medication use, the algorithms listed below will be followed. Start and stop dates of AEs or concomitant medication will be displayed as reported in the subject data listings (ie, no imputed values will be displayed in data listings).

- Missing start day, but month and year present:

If the start of study medication occurred in the same month and year as the occurrence of the AE/concomitant medication, the start day of the event/concomitant medication will be assigned to the day of first intake of study medication. Otherwise the start day will be set to the 1st day of the month.

- Missing start day and month, but year present:

If the start of study medication occurred in the same year as the occurrence of the AE/concomitant medication, the start day and month will be assigned to the date of first intake of study medication. Otherwise the start day and month will be set to January 1st.

- Missing end day, but month and year present:

The end day will be set to the last day of the month.

- Missing end day and month, but year present:

The end day and month will be set to the maximum of the date of study termination or the date equivalent to 28 days after last intake of study medication.

However, if the study termination year and year for the date which is 28 days after last intake of study medication are greater than the event/concomitant medication year, the day and month are to be set to December 31st.

#### **4.2.3 Definition of concomitant medication in case of missing dates**

With respect to definition of medication as concomitant, the following rule will be applied in case of completely missing stop and/or start date information:

Medications, excluding AEDs, with a missing start date whose stop date is either unknown or after the date of the first dose of study medication will be considered as concomitant medication.

AEDs with a missing start date whose stop date is unknown will be considered as lifetime AEDs. AEDs with a missing start date whose stop date is after the date of first dose of study medication will be considered concomitant.

Medications, including AEDS, with a missing start date whose stop date is prior to first intake of study medication will not be considered concomitant.

In subject data listings, dates will be displayed as reported.

#### **4.2.4 Incomplete dates for the last administration of study medication**

For purposes of imputing missing components of partially reported dates for the last administration of study medication, the algorithms listed below will be followed. Stop dates of study medication will be displayed as reported in the subject data listings (ie, no imputed values will be displayed in data listing).

- Missing last administration day, but month and year present:  
The last administration day will be set to the last day of the month or the date of the final contact, whichever is earlier in the month.
- Missing last administration day and month, but year present:  
The last administration day will be set to the last day of the year or the date of the final contact, whichever is earlier in the year.
- Completely missing date of last administration:  
For calculating the duration of exposure, if the date of last administration is completely missing and no information could be obtained from data cleaning exercises, the date of last administration should be imputed as the date of last contact according to the Study Termination eCRF module. For all other purposes, no imputation will be done if the date of last administration is completely missing.

If a subject died during the study, and the imputed last administration date according to the rules above is after the date of death, the last administration date will be assigned to the date of death.

#### **4.2.5 Incomplete dates for seizure diary data**

Seizure frequency and seizure-free days will be calculated over non-missing diary days during each time interval; days for which seizure diary data were not obtained will not be considered in the calculation of seizure frequency or seizure-free days. If more than 10% of the diary entries are missing for a specific subject and time interval, then that subject will not be considered for the calculation of seizure frequency or seizure-free days during that time interval.

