#### Maintenance Period

The day after the end of the Titration Period (Visit 5) and prior to or on the end date of the Maintenance Period (Visit 8) for subjects who complete the Maintenance Period, or the day after the end of the Titration Period (Visit 5) and prior to or on the date of the ETV for subjects who

discontinue during the Maintenance Period. If a subject does not have a Visit 8/ETV, then either the date of the last scheduled or unscheduled visit during the Maintenance Period or the date of last known dose of study medication during the Maintenance Period, whichever is later, will define the end date of the Maintenance Period.

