## **8 EFFICACY ANALYSES**

The primary and secondary efficacy variables will be measured using data obtained from the subject diary. Subjects or parents/caregivers will keep a diary to record the daily seizure activity from the beginning of the Baseline Period until the last visit, recording both seizure type, seizure frequency, and whether the seizures were a cluster.

Each seizure code in the clinical database will be mapped to exactly 1 of the ILAE seizure codes based on the 1981 ILAE classification (Seizure Count eCRF).

The assessment of efficacy is based on seizure frequency, and will be analyzed primarily for the FAS. All CIs presented will be 95% 2-sided CIs.

For subjects who prematurely discontinue from the study, last observation carried forward method as described in section 4.2 will be applied to obtain a seizure frequency estimate for the Maintenance Period.

All efficacy variables will be listed.

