### **8.1 Statistical analysis of the primary efficacy variable**

#### **8.1.1 Derivations of primary efficacy variable**

The primary efficacy variable is the change in partial-onset seizure frequency per 28 days from Baseline to the Maintenance Period. Seizure frequency per 28 days will be based on the number of days for which seizure information was provided during the specified time interval.

Seizure frequency per 28 days will be calculated as  $([\text{number of seizures over the specified time interval}] \text{ divided by } [\text{number of days in the interval}])$  multiplied by 28.

The partial-onset seizure frequency per 28 days will be calculated for both the Baseline Period and for the Maintenance Period, and the change from Baseline calculated.

If a seizure cluster is reported, the highest recorded daily seizure frequency during the Treatment Period for the seizure type associated with the report of a seizure cluster will be used as the imputed seizure frequency for the day on which the cluster occurred.

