### **8.1.2 Primary analysis of the primary efficacy variable**

Seizure frequency will be analyzed using analysis of covariance (ANCOVA) with terms for treatment and center (pooled appropriately), on log-transformed seizure frequency using the transformation of  $\ln(X+1)$ , where X is the seizure frequency. Log transformed Baseline seizure frequency will be used as a covariate. Assumptions for the parametric model will be evaluated by diagnostic (eg, Shapiro-Wilk test for normality) and graphical methods such as residual plots, including normal probability plots, histograms, and plots of residuals versus Baseline covariate values and treatment. An assessment will be made with regards to the influence of individual observations (eg, extreme outliers) on the analysis. To the extent feasible, such potential influential observations will be identified prior to unblinding, and an assessment will be made with regard to the potential impact of such data, including the evaluation of alternative statistical methodology such as non-parametric methods. If deemed that a non-parametric method is warranted, an ANCOVA model on rank of seizure frequency per 28 days with terms for treatment and center (pooled appropriately) will be employed as the primary analysis. Ranked seizure frequency per 28 days during the Baseline Period will be used as a covariate.

The seizure frequency between treatment and placebo will be compared using the least squares means (LSMs). The percent reduction over placebo will be estimated as  $100 \times (1 - \exp[\text{LSM}_{\text{LCM}} - \text{LSM}_{\text{placebo}}])$ . A 95% CI will also be calculated for the percent reduction over placebo.

Partial-onset seizure frequency per 28 days during the Baseline Period and during the Maintenance Period, and the change from Baseline will be summarized by treatment group. This summary will be repeated by treatment group and age group, using the levels defined in section 4.8.

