### **8.1.4 Supportive and sensitivity analyses of the primary efficacy variable**

The impact of missing data on the primary efficacy analysis will be evaluated by repeating the primary analysis of the primary efficacy variable detailed in section 8.1.2 on observed cases.

For subjects who prematurely discontinue from the study, only data recorded up to their ETV will be used to obtain a partial-onset seizure frequency estimate for the Maintenance Period.

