### **8.2.1 Change in partial-onset seizure frequency per 28 days from Baseline to entire Treatment Period**

The partial-onset seizure frequency per 28 days will be calculated for both the Baseline Period and for the entire Treatment Period, as detailed in section 8.1.1. The change from Baseline will also be calculated.

The change in partial-onset seizure frequency per 28 days from Baseline to the entire Treatment Period will be analyzed as detailed in section 8.1.2.

Partial-onset seizure frequency per 28 days during the Baseline Period and during the entire Treatment Period, and change from Baseline will be summarized by treatment group. This summary will be repeated by treatment group and age group, using the levels defined in section 4.8.

The change in seizure frequency per 28 days from Baseline to the Treatment Period, defined as the combined Titration and Maintenance Periods, will be summarized by treatment group (LCM or placebo) using descriptive statistics. Statistical testing will be performed using an ANCOVA model with terms for treatment and pooled site and baseline seizure frequency as a covariate.

The change in seizure frequency by period will also be summarized using descriptive statistics by treatment group and seizure type.

The change in seizure frequency by visit will also be summarized, based on observed analysis. For each visit during the Titration Period, the LCM treatment group will be compared to placebo in an exploratory onset of efficacy analysis. Statistical testing will be performed using an ANCOVA model with terms for treatment and pooled site and baseline seizure frequency as a covariate using data recorded at each individual Titration Period visit.

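### SAP 4.2.5 drops FAS subjects with more than 10% of diary days missing from the primary ANCOVA, and no planned analysis of the primary variable tests what that does to the estimate

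*SAP*

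**What the plan says.** SAP 4.2.5 first bases seizure frequency on recorded diary days only, then adds an exclusion: "If more than 10% of the diary entries are missing for a specific subject and time interval, then that subject will not be considered" when frequency or seizure-free days are derived for that interval.

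The other relevant provisions are these:

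- **Analysis set.** The FAS (SAP 3.5.2) needs randomisation, one dose, and that the subject "had a Baseline and at least 1 post-Baseline assessment of seizure frequency data". It sets no minimum diary completeness.
- **Derivation.** SAP 8.1.1 already allows for gaps: "Seizure frequency per 28 days will be based on the number of days for which seizure information was provided during the specified time interval".
- **Primary model.** SAP 8.1.2 fits an ANCOVA to ln(X+1) of the Maintenance frequency, with the log-transformed Baseline frequency as covariate. A rank ANCOVA may replace it.
- **Carry-forward.** SAP 8 limits it to dropouts: "For subjects who prematurely discontinue from the study, last observation carried forward method as described in section 4.2 will be applied".
- **Other analyses of the primary variable.** SAP 8.1.3 repeats the model on the PPS. SAP 8.1.4 repeats it on observed cases, where for dropouts "only data recorded up to their ETV will be used to obtain a partial-onset seizure frequency estimate for the Maintenance Period".
- **Protocol 13.6** promises sensitivity analyses of the impact of missing data on primary efficacy and leaves the details to the SAP.

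**The concern.** A subject without a Baseline or a Maintenance frequency cannot enter the ANCOVA, and nothing in the SAP supplies a value for a completer with a sparse diary. The set actually analysed can therefore be smaller than the FAS that the plan names as primary.

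The two kinds of removal differ. Baseline diary gaps are fixed before randomisation, so losing those subjects costs power but does not favour an arm. Maintenance gaps arise after randomisation. If keeping the diary is related to how a child is doing, and that relation or the number of gaps differs between arms, the comparison can be biased.

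The planned by-arm summaries (Baseline, Maintenance "and the change from Baseline will be summarized by treatment group") carry an n, so a reader could see that subjects are absent. No planned analysis would show whether the primary estimate depends on their absence.

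**Working it through.** **Inputs.** From the SAP and protocol: Baseline 8 weeks (56 days), Titration 6 weeks (42), Maintenance 10 weeks (70); difference -0.249, SD 0.73, two-sided 5%, 80% power, 135 per arm, 154 per arm enrolled (SAP 2.4). Assumed, because the documents give no figure: 5% to 10% of subjects removed, the outcomes of removed subjects, and 10 seizures per 28 days for the precision check.

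**1. The plan's own figure.** n = 2 × (1.960 + 0.842)² × (0.73/0.249)² = 134.9, so 135 per arm. This matches. The sample size is not in dispute.

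**2. Where the rule bites (nominal period lengths).**
- Maintenance: 10% of 70 = 7, so removal starts at 8 missing days (62 recorded).
- Baseline: 10% of 56 = 5.6, so removal starts at 6 missing days (50 recorded).
- Whole Treatment Period: 10% of 112 = 11.2, so removal starts at 12 missing days.

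**3. Does any planned analysis lift the rule?**
- PPS: a subset of the FAS, so it cannot restore anyone.
- Observed cases: changes only the handling of discontinuers and uses the same derived frequency.
- Rank ANCOVA: ranks that same frequency.
- Treatment Period ANCOVA (SAP 8.2.1, "The change in partial-onset seizure frequency per 28 days from Baseline to the entire Treatment Period will be analyzed as detailed in section 8.1.2"): readmits a completer with 8 to 11 missing Maintenance days and a full Titration diary, but for another endpoint. It does not help Baseline failures.
- By-visit summaries (SAP 8.2.1, 8.2.4, 8.2.7): may include such subjects at some visits, but do not re-estimate the primary effect.

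**4. Power** (noncentral t, effect size 0.249/0.73).

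| Removed | n per arm | Power |
|---|---|---|
| 0% | 154 | 84.7% |
| 5% | 154 × 0.95 = 146.3 | 82.8% |
| 10% | 154 × 0.90 = 138.6 | 80.8% |

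The base is 154 because discontinuers with seizure data stay in through carry-forward.

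**5. Possible shift in the estimate.** With s the share removed and d the mean of removed minus retained subjects in an arm (L = lacosamide, P = placebo), all-FAS effect = analysed effect + s_L × d_L − s_P × d_P. SE = 0.73 × √(2/154) = 0.083.
- Removed lacosamide subjects had no benefit (d_L = 0.249, d_P = 0). At 5%: -0.249 + 0.0125 = -0.237, a 21.1% reduction over placebo instead of 22.0%, or 0.15 SE. At 10%: -0.249 + 0.0249 = -0.224, a 20.1% reduction, or 0.30 SE.
- Unequal removal, 10% in one arm and 5% in the other, with removed subjects 0.5 log units higher or lower in both: the shift is (0.10 − 0.05) × 0.5 = 0.025 either way, so -0.224 to -0.274 (20% to 24%).

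**6. What the removed rates are worth.** At 10 seizures per 28 days, the Poisson SD of ln(X+1) is 0.186 from 70 days and 0.199 from 62 days, against a planned total SD of 0.73. A 62-day rate is nearly as precise as a full one.

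**7. Completers against dropouts.** For those who leave within Maintenance, SAP 3.2.2 closes the period at the early termination visit: "the day after the end of the Titration Period (Visit 5) and prior to or on the date of the ETV for subjects who". On that reading, a dropout with 9 of 10 days recorded has exactly 10% missing and stays, with a Poisson SD of about 0.66. A completer with 62 of 70 recorded (11.4% missing) goes.

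**The case against.** The strongest reply is that the rule is pre-specified, applies alike to both arms, and on the figures above changes little. That stands, and it sets the weight of the point. The trial also has real safeguards. Inclusion criterion 2 asks for ability to complete diaries (Protocol 6.1), diary use is confirmed at every visit and call (7.7), the Baseline diary is reviewed before randomisation (8.1.3), and the investigator checks daily completion (9.2.1). These may keep the number small, but the documents give no rate and the safeguards do not test the estimate.

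SAP 4.2.5 does not literally say that anyone leaves the ANCOVA. That follows because no frequency exists and no imputation is given. Nor does it state the denominator for dropouts, so step 7 rests on reading it with 3.2.2.

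A reader might infer two stronger things that the documents do not support:

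- **That SAP 3.9 hides a departure from the protocol.** The protocol sets no threshold for intermittent gaps and leaves detail to the SAP. The 10% rule elaborates; it does not contradict.
- **That the 20% limit in SAP 8.2.9 contradicts the 10% limit.** It governs seizure-free status in completers, a different and descriptive endpoint. Different tolerances for different endpoints are not an inconsistency.

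**Conclusion.** The point holds as a gap in the sensitivity analyses, not as a flaw that undermines the primary result. FAS completers can leave the primary ANCOVA after randomisation because of diary gaps, and no analysis of the primary variable shows what difference that makes, although Protocol 13.6 promises such an evaluation.

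A reader might conclude that the trial is underpowered or its estimate seriously biased. The figures do not support that: power stays at or above 80.8% from 154 per arm, and the shift is 0.15 to 0.30 SE in the no-benefit case. Those figures depend on the assumed 5% to 10% removed and on the assumed outcomes of removed subjects. More frequent or more uneven gaps would give larger shifts.

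This is a cheap improvement worth making.

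**What to change.** - **Add to SAP 8.1.4** one pre-specified repeat of the primary ANCOVA in FAS subjects, using seizures per recorded diary day × 28, without the 10% exclusion.
- **If a minimum number of recorded days is wanted,** fix it before unblinding and apply the same minimum to completers and discontinuers. A floor for completers alone would recreate the imbalance in step 7.
- **Tabulate** the subjects removed under 4.2.5 by arm and by interval.
- **Optional:** a sentence in SAP 8.2.2 saying whether a subject without a Maintenance frequency counts as a non-responder. The section's catch-all wording suggests so, but does not mention this case.

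The cost is SAP wording, one table and one extra model run on data already collected, with no protocol change. The statistical price is that some subjects contribute less precise rates: slightly so near the threshold (0.199 against 0.186), more so for very sparse diaries (0.31 from 28 days at the same assumed rate).
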